### **5.3. Covariate Adjustment**

The randomization to treatment groups at Week 0 (Visit 2) is stratified by disease severity (IGA) and geographic region as described in Section 4.1. Unless otherwise specified, the statistical analysis models will adjust for disease severity and geographical region. When an MMRM analysis is performed, baseline value and baseline-by-visit interactions will be included as covariates.

### **5.4. Handling of Dropouts or Missing Data**

Nonresponder imputation (for categorical variables) and MMRM (for continuous variables) will be the primary methods used to handle missing data. Subjects who receive rescue therapy will be considered missing at rescue and all subsequent visits.

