7.7.3. Rescue Therapy

Rescue therapy is permitted **starting at Week 8** for subjects who do not achieve an EASI-25 response. If the subject meets criteria, the decision to implement rescue is according to investigator judgment and is not a requirement. Rescue therapy should only be initiated at a visit at which an EASI-25 is not met.

Choice of rescue therapy treatment

- Triamcinolone 0.1% cream and/or hydrocortisone 2.5% ointment. In the event where either of these topical formulations is not available, an alternate, equivalent potency TCS cream and/or ointment may be used.
- Investigators may also select to use TCNI and/or crisaborole where approved. If TCNI are prescribed, use should be limited to problem areas only (e.g., face, neck, skin folds, genital areas, etc.).
- On the days of study visits, topical therapy should not be applied before the subject has undergone all study procedures and clinical evaluations in order to allow adequate assessment of skin dryness.
- Subjects rescued to topical therapy will continue to take IP and use of rescue therapy will be documented in the eCRF.

In subjects who do not improve sufficiently with the prescribed provided rescue topical therapy after 7 days, a higher potency TCS may be used and IP may continue. It is recommended that if a subject reaches “clear” to “almost clear” skin after topical rescue, then medium- and/or high-potency TCS and TCNI should be stopped, and low-potency TCS (e.g., hydrocortisone 2.5% ointment) should be used once daily for an additional 7 days, then stopped. If lesions return, subjects can be retreated with TCS with or without TCNI and/or crisaborole as before at the discretion of the investigator.

If topical rescue therapy as described above fails to sufficiently control AD symptoms and if the investigator determines that a subject requires treatment with another therapeutic agent that has been demonstrated to be effective for treatment of AD but is contraindicated in this study, the subject should be discontinued from the study. In such cases, discontinuation from the study occurs prior to introduction of the new agent.

Note that subjects who receive rescue therapy during the induction period will be considered nonresponders for the primary analysis, but will undergo re-assignment/re-randomization at Week 16 based on EASI-50 response according to Section 5.1, and will not automatically be considered nonresponders for purposes of treatment assignment.

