Investigators should make every attempt to conduct efficacy and safety assessments immediately before administering any rescue treatment. An unscheduled visit can be used for this purpose if necessary.

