10.2.1.1. Missing Data Imputation

- Nonresponder imputation (NRI): All subjects who discontinue the study or the study treatment at any time for any reason will be defined as nonresponders for the analysis of categorical efficacy variables at discontinuation and subsequent visits. Subjects who receive rescue therapy will be analyzed as nonresponders at rescue and subsequent visits.
- MMRM: Continuous variables will be assumed to be missing after rescue or discontinuation for which an MMRM analysis will be performed.

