### **5.2.2. Definition of Baseline and Postbaseline Measures**

The baseline value for the efficacy and health outcomes for the Induction and Maintenance Periods is defined as the last non-missing measurement on or prior to the date of first study drug administration (expected at Week 0, Visit 2). The baseline value for the daily diary assessments (Itch NRS, Skin Pain NRS) is defined as the average of the non-missing assessments in the last 7 days prior to the date of first study drug administration (expected at Week 0, Visit 2). Criteria for derivation of the weekly average requires that there must be at least 4 non-missing measurements in the 7 days indicated, otherwise, an expanded window of 14 days prior to first study drug administration, if available, may be utilized in order to obtain the most recent 4 non-missing measurements prior to first study drug administration (ie, Day -14 to Day -1). If there are not at least 4 non-missing assessments collected prior to the date of first study drug

administration using the aforementioned method, then the baseline will be designated as missing. Other definitions of baseline value, such as the last measurement on or prior to rescue, may be used to conduct additional supporting analyses.

Postbaseline measurements are collected after study drug administration through Week 60 (Visit 801) or early discontinuation visit. For data collected in the electronic Clinical Outcomes Assessment (eCOA) tablet (including Patient-Reported Outcomes [PRO] and Clinician-Reported Outcomes [ClinRO]) and related to efficacy assessments, unscheduled postbaseline visits that fall within the visit windows defined by Lilly will be summarized in the by-visit analyses if there is no scheduled visit available. That is, a  $\pm 2$  day window is applied to Visit 3 (Week 1), Visit 4 (Week 2), and Visit 5 (Week 4), and a  $\pm 4$  day window is applied to Visit 6 (Week 8), Visit 7 (Week 12), and Visit 8 (Week 16), as well as to every visit in the Maintenance Period. If there is more than 1 unscheduled visit within the defined visit window and no scheduled visit is available, the unscheduled visit closest to the scheduled visit date will be used.

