### **5.2.3. Analysis Methods**

The main analysis of categorical efficacy variables and health outcomes variables will use a logistic regression analysis with region, baseline disease severity (IGA) and treatment group in the model. The p-value and 100(1-alpha)% CI for the odds ratio from the logistic regression model are used for primary statistical inference. The difference in percentages and 100(1-alpha)% CI of the difference in percentages using the Newcombe-Wilson without continuity

correction will be reported. The p-value from the Fisher's exact test will also be produced as a secondary analysis.

The main analysis for all continuous efficacy and health outcomes variables will use mixed model repeated measures (MMRM) analysis. The MMRM model will use a restricted maximum likelihood (REML) estimation. The model will include treatment, region, baseline disease severity, visit, and treatment-by-visit-interaction as fixed categorical effects and baseline and baseline-by-visit-interaction as fixed continuous effects. An unstructured (co)variance structure will be used to model the between- and within-patient errors. If this analysis fails to converge, the heterogeneous autoregressive [ARH(1)], followed by the heterogeneous compound symmetry (CSH), followed by the heterogeneous Toeplitz (TOEPH) will be used. The Kenward-Roger method will be used to estimate the degrees of freedom. Type III tests for the least-squares means (LSM) will be used for the statistical comparison. The LSM difference, standard error, p-value and 100(1-alpha)% CI will also be reported.

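### SAP 5.4 sets the rescue-visit EASI to missing, whereas the protocol removes only later values; the discarded value gates rescue, so missing-at-random fails

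*SAP*

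**What the plan says.** Protocol section 10.2.1.1 gives two timing rules. For categorical endpoints: "Subjects who receive rescue therapy will be analyzed as nonresponders at rescue and subsequent visits". For continuous endpoints: "Continuous variables will be assumed to be missing after rescue or discontinuation for which an MMRM analysis will be performed".

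SAP section 5.4 names nonresponder imputation and MMRM as the two methods and then gives one rule for both: "Subjects who receive rescue therapy will be considered missing at rescue and all subsequent visits". SAP 5.4.2 adds no exception for MMRM. It states that the model assumes data are missing at random, meaning that missingness relates to observed data. SAP 5.4.1 gives no visit timing for the categorical rule.

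Protocol section 7.7.3 fixes how rescue relates to the assessment. Rescue is allowed from Week 8, and "Rescue therapy should only be initiated at a visit at which an EASI-25 is not met". It also says "On the days of study visits, topical therapy should not be applied before the subject has undergone all study procedures and clinical evaluations", and "Investigators should make every attempt to conduct efficacy and safety assessments immediately before administering any rescue treatment". SAP 5.2.2 treats the rescue-visit value as usable: "Other definitions of baseline value, such as the last measurement on or prior to rescue, may be used".

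**The concern.** EASI is scheduled at Weeks 8, 12 and 16, the induction visits at which rescue can start. The value at the rescue visit is a planned measurement taken before rescue. It is also the gate: a patient who meets EASI-25 at a visit should not start rescue there.

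If that value is kept, later missingness depends on something the model sees. If it is deleted, missingness depends on the deleted value. The model then infers a rescued patient's Week 16 EASI from earlier visits, without the poor result that led to rescue, and each arm's mean looks better than it is. If placebo patients are rescued more often and variability is similar across arms, the difference from placebo shrinks. Where rescue starts at the Week 16 visit, the endpoint value itself is lost.

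Change in EASI and change in SCORAD are secondary endpoints analysed this way, in a study meant to guide dose selection. The SAP plans no sensitivity analysis for departures from missing-at-random.

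**Working it through.** **The plan's own figure.** The only stated design figure is at least 90% power on the primary endpoint. Enumerating the 2-sided Fisher's exact test for 50 per arm and 36% versus 8% gives 91.4%, which agrees. The rescue rule for MMRM does not touch it. The documents give no EASI effect, SD or rescue rate.

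**Why missing-at-random fails.** Let rescue at visit v occur with probability q if improvement at v is under 25%, and otherwise not at all.
- Protocol rule: EASI at v stays in the data, so missingness after v depends on an observed value.
- SAP rule: EASI at v is removed, so missingness from v depends on the removed value. Suppose a fraction f of patients with a given history fail EASI-25 at v. Among those retained the fraction is f(1−q)/(1−fq). With q = 0.5 this is 0.5f/(1−0.5f), which is below f whenever 0 < f < 1. The retained patients are a favourable selection.

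**Simulation A (two arms, 200,000 each).** Assumptions: baseline EASI mean 30, minimum 16; SD of change 12; AR(1) correlation 0.6 or 0.85 per visit step; placebo change at Week 16 about −9; visits at Weeks 2, 4, 8, 12 and 16; rescue at Week 8, 12 or 16 with uptake 25%, 50% or 80%. The fit is maximum likelihood with an unstructured covariance. Week 16 differences are shown as full data / protocol rule / SAP rule. Understatement = 1 − SAP/full.

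| Correlation, uptake | True −6 | SAP understates | True −10 | SAP understates |
|---|---|---|---|---|
| 0.6, 25% | −5.91 / −5.89 / −5.56 | 5.9% | −10.00 / −10.01 / −9.39 | 6.1% |
| 0.6, 50% | −6.00 / −5.95 / −4.95 | 17.5% | −9.94 / −9.97 / −8.23 | 17.2% |
| 0.6, 80% | −6.01 / −6.05 / −3.76 | 37.4% | −9.94 / −9.98 / −6.44 | 35.2% |
| 0.85, 25% | −5.95 / −5.95 / −5.74 | 3.5% | −10.09 / −10.11 / −9.73 | 3.6% |
| 0.85, 50% | −6.05 / −6.07 / −5.45 | 9.9% | −9.99 / −10.02 / −8.99 | 10.0% |
| 0.85, 80% | −6.00 / −5.95 / −4.51 | 24.8% | −10.07 / −10.11 / −7.88 | 21.7% |

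The protocol rule stays within 0.1 points of the full-data fit throughout. The SAP rule overstates placebo improvement by about 1.0 to 7.4 points. With no treatment effect the difference moves by less than 0.1.

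**Simulation B (four arms).** Assumptions: mean improvement 35/45/55/65% or 25/40/50/60% from placebo to highest dose; patient SD of fractional improvement 0.32 with visit noise 0.15, or 0.25 with 0.25; baseline EASI at least 16, median about 28; uptake 30%, 50% or 80%, with or without rescue starting at Week 16. One unstructured covariance is shared by all arms, following SAP 5.2.3 ("An unstructured (co)variance structure will be used to model the between- and within-patient errors"). Region and IGA terms were omitted. Bias is measured against the same model on complete data, in 200 trials of 400 per arm.

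| Setting | SAP rule | Protocol rule |
|---|---|---|
| Equal variability, 30-50% uptake, no Week 16 rescue | −1 to −8% | 0 to −3% (both 30-50% rows) |
| Equal variability, 30-50% uptake, Week 16 rescue | −4 to −18% | as above |
| Equal variability, 80% uptake | −15 to −38% | −3 to −6% |
| Drug-arm SD 1.4 times placebo | −9 to +6% | −1 to +9% |
| Drug-arm SD about 2 times placebo | −5 to +23% | +2 to +25% |

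At 30-50% uptake and equal variability, the SAP rule overstates improvement by 0.5-2.9 points on placebo and 0.25-1.3 on the highest dose. The protocol rule overstates placebo by at most 0.25. Rescue at Week 16 removes a further 6-9 percentage points of placebo Week 16 values. With no effect the difference moves by 0.05 points or less.

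*Example:* 35/45/55/65%, 50% uptake, Week 16 rescue allowed. Rescued: 43/33/26/18%. True highest-dose difference: 8.2 points. Protocol rule: 8.2 × (1 − 0.026) = 8.0. SAP rule: 8.2 × (1 − 0.122) = 7.2. The gap is about 0.8 points. At 50 per arm (1000 trials) the SE is about 2.0, so the gap is 0.8/2.0 = 0.4 SE.

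A further run with 100,000 per arm and equal variability gave 3-17% understatement under the SAP rule at 30-50% uptake and 15-36% at 80%. The protocol rule gave 0.5-2.6% and 2-5.5%.

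**The case against.** - **Ambiguity.** The SAP sentence is generic, and being missing at rescue could be read as from the start of rescue, which would keep the pre-rescue value. SAP 5.2.2 fits that reading. But the literal reading is more natural, nothing in SAP 5.4.2 narrows it, and a programmer would follow it. Either way the sentence needs changing.
- **Protocol latitude.** Protocol 10.2.1 leaves MMRM detail to the SAP and allows non-principal changes to be justified in the study report. That stands: the mismatch alone is minor, and the missing-at-random argument carries the point.
- **Discretion.** Rescue is the investigator's choice, so the EASI value gates rescue and does not alone decide it. That stands, but the argument needs only the gate. Keeping the value restores missing-at-random only as far as the choice depends on data in the model.
- **SCORAD.** Its MMRM does not include EASI, so its missingness depends on something outside the model under either rule. That stands, and the SCORAD effect was not simulated.
- **Unequal variability.** With drug-arm SD about twice placebo, the protocol rule is not uniformly better. One set of runs at that ratio put it at +3% to +10%, against −7% to +1.5% for the SAP rule. That stands: one common covariance is then wrong and neither rule is unbiased.
- **Size.** The largest figures need 80% uptake of an optional treatment. Rescue started between scheduled visit windows gives the same by-visit data under both rules, which lowers the effect. Both are fair limits on the size and leave the direction under equal variability unchanged.

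**Conclusion.** The concern holds. The SAP's rule for continuous endpoints differs from the protocol's, without a stated reason, and it deletes a valid EASI value on which missingness depends. That contradicts the assumption the SAP states for its own model.

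Under equal variability, the Week 16 EASI difference is understated by about 1-18% at 30-50% uptake and 15-38% at 80%. Most of this goes away under the protocol rule. These sizes are illustrative, since rescue rates, effects and SDs are all assumed. With more variable drug arms the direction can reverse. By-arm means are too favourable wherever patients are rescued, placebo included, when variability is equal.

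The consequence is moderate: about 0.4 SE at the planned sample size in the worked example. The primary IGA endpoint and EASI-50/75/90 are unaffected, because rescued patients count there as nonresponders. The change should be made, but the trial's main conclusion does not depend on it.

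**What to change.** Replace the single sentence in SAP 5.4 with two:

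> For categorical endpoints, a rescued patient counts as a nonresponder from the visit at which rescue starts. For continuous endpoints analysed by MMRM, values recorded at that visit before first use of rescue are kept, and values recorded after first use are set to missing.

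The first sentence is needed because SAP 5.4.1 gives no timing. State also that assessments at the visit where rescue starts are taken as pre-rescue unless the record shows otherwise, since a start date alone cannot order events on the same day. A pre-rescue value from an unscheduled visit outside the windows in SAP 5.2.2 stays out of the by-visit model under either rule.

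If the sponsor prefers to keep the present rule, the SAP should give the reason and add a sensitivity analysis that does not assume missing-at-random.

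The cost is two SAP sentences and one programming flag. No new data are needed, and trial conduct does not change.

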#### **5.4.1. Nonresponder Imputation**

For the analysis of categorical efficacy and health outcomes variables such as IGA(0,1) and EASI50/75/90, the primary method to impute missing data will be a nonresponder imputation (NRI) method.

All categorical endpoints will utilize the NRI method to patients who permanently discontinued study drug or were rescued.

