5.1. Overall Design

Study I9N-MC-FCAB (FCAB) is a Phase 2, multicenter, randomized, double-blind, placebo-controlled, parallel-group, outpatient study evaluating the efficacy and safety of LY3375880 SC 600 mg Q4W, 150 mg Q4W, and 50 mg Q4W as compared to placebo Q4W in adult subjects with moderate-to-severe AD. In addition, LY3375880 300mg Q4W will be evaluated in the maintenance period as described below.

The study duration will be up to 65 weeks over 4 study periods:

- Period 1: Screening Period lasting from 8 to 35 days prior to Week 0 (baseline, Visit 2).
- Period 2: Induction Period, lasting from Week 0 (baseline, Visit 2) through Week 16 (Visit 8).
- Period 3: Maintenance Period, lasting from Week 16 (Visit 8) through Week 52 (Visit 17, inclusive). At Week 16, the following will occur:
 - Responders (defined as having achieved a 50% reduction in the Eczema Area and Severity Index score [EASI-50] response, regardless of whether rescue therapy has been initiated) will undergo the following re-randomizations:
 - Subjects on any dose of LY3375880 will be re-randomized at a 2:1 ratio to either maintain their current regimen or to receive placebo until loss of response (not achieving a 25% reduction in the EASI score [EASI-25] at a scheduled visit), at which point they will restart their induction period regimen.
 - Subjects on placebo will continue receiving placebo until loss of response, at which point they will be reassigned to receive LY3375880 at 300 Q4W.
 - Nonresponders will undergo the following reassessments:
 - Subjects on 50 mg Q4W will be reassigned to 150 mg Q4W.
 - Subjects on 150 mg Q4W will be reassigned to 300 mg Q4W.
 - Subjects on 600 mg Q4W will remain on their current regimen.
 - Subjects on placebo will be reassigned to receive 300 mg Q4W.
 - Subjects with persistent disease activity, defined as not achieving EASI-25 for 3 consecutive scheduled maintenance period visits, not already on 600 mg Q4W will be reassigned to 600 mg Q4W for the remainder of the study.
- Period 4: Post-Treatment Follow-Up Period, spanning approximately 8 weeks from Week 52 (after Visit 17) to Week 60 (Visit 801).

Rescue therapy is permitted starting at Week 8 for subjects who do not achieve an EASI-25 response. Refer to Section [7.7.3](#) for details.

Treatment Arms and Duration:

[figure not shown]

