10.2.1.2. Maintenance Period Considerations

For maintenance period efficacy measures, unless otherwise stated, baseline will be the last available value before the initial randomization in the induction period, which in most cases will be the value recorded at Week 0 (Visit 2).

For maintenance period safety measures, unless otherwise stated, baseline will be the last available value before the initial dose in the maintenance period, which in most cases will be the value recorded at Week 16. Additional information on baseline for efficacy and safety analyses will be available in the SAP.

Maintenance phase analyses are exploratory; therefore, only descriptive statistics will be provided. Change from baseline and 95% CI will be calculated by treatment for continuous variables. The proportion and 95% CI will be reported by treatment for categorical variables.

Additional sensitivity analyses for the primary and key secondary endpoints may be done and will be specified in the SAP.

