## 4. Study Design

### 4.1. Summary of Study Design

Study I9N-MC-FCAB(b) (FCAB) is a Phase 2, multicenter, randomized, double-blind, placebo-controlled, parallel-group, outpatient study evaluating the efficacy and safety of LY3375880 subcutaneous (SC) 600 mg every 4 weeks (Q4W), 150 mg Q4W, and 50 mg Q4W as compared to placebo Q4W in adult subjects with moderate-to-severe AD. In addition, LY3375880 300mg Q4W will be evaluated during the maintenance period. The study duration will be up to 65 weeks over 4 study periods:

[figure not shown]
- Period 1: Screening Period lasting from 8 to 35 days prior to Week 0 (baseline, Visit 2).
- Period 2: Induction Period, lasting from Week 0 (baseline, Visit 2) through Week 16 (Visit 8), inclusive.
  - An internal assessment committee will conduct an unblinded interim analysis of efficacy safety data when approximately 40%-60% of patients complete Week 16 (Visit 8). This interim analysis will be conducted for internal decision making to trigger planning activities for future studies associated with LY3375880.
- Period 3: Maintenance Period, lasting from Week 20 (Visit 9) through Week 52 (Visit 17), inclusive. At Week 20, the following will occur:
  - Responders (defined as having achieved a 50% reduction in the Eczema Area and Severity Index score [EASI-50] response, regardless of whether rescue therapy has been initiated) will undergo the following re-randomizations:
    - Subjects on any dose of LY3375880 will be re-randomized at a 2:1 ratio to either maintain their current regimen or to receive placebo until loss of response (not achieving a 25% reduction in the EASI score [EASI-25] at a scheduled visit), at which point they will restart their induction period regimen.
    - Subjects on placebo will continue receiving placebo until loss of response, at which point they will receive LY3375880 300 mg Q4W.
  - Nonresponders will undergo the following re-randomizations/reassignments:
    - Subjects on 50 mg Q4W will be reassigned to 150 mg Q4W
    - Subjects on 150 mg Q4W will be reassigned to 600 mg Q4W
    - Subjects on 600 mg Q4W will remain on their current regimen
    - Subjects on placebo will receive LY3375880 300 mg Q4W.
  - Subjects with persistent disease activity defined as not achieving EASI-25 for 3 consecutive maintenance period visits, or 8 maintenance period weeks (whichever is longer) not already on 600 mg Q4W will be reassigned to 600 mg Q4W for the remainder of the study.

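### Nonresponder imputation ignores the plan's own failure-triggered drug switches in maintenance, and Week 52 groups are undefined, so response after a switch can count for the regimen that failed

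*SAP*

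**What the plan says.** **Nonresponder rule.** SAP 5.4.1: "All categorical endpoints will utilize the NRI method to patients who permanently discontinued study drug or were rescued". Protocol 10.2.1.1 makes discontinuation of study or treatment a nonresponse and adds: "Subjects who receive rescue therapy will be analyzed as nonresponders at rescue and subsequent visits". Under the same section, continuous values become missing only after rescue or discontinuation.

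**What rescue is.** Protocol 7.7.3 defines it as topical treatment, allowed from Week 8 at a visit where EASI-25 is not met: "Subjects rescued to topical therapy will continue to take IP and use of rescue therapy will be documented in the eCRF". A planned change of study drug is therefore not rescue.

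**Failure-triggered switches in maintenance** (Protocol 5.1 and SAP 4.1):
- An LY3375880 responder re-randomized to placebo who loses response (EASI-25 not met at a scheduled visit) goes back on active drug: "at which point they will restart their induction period regimen".
- A placebo responder who loses response starts active drug: "Subjects on placebo will continue receiving placebo until loss of response, at which point they will receive LY3375880 300 mg Q4W".
- A subject with persistent disease activity "not already on 600 mg Q4W will be reassigned to 600 mg Q4W for the remainder of the study".

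Placebo nonresponders at the end of induction also change drug: "Subjects on placebo will be reassigned to receive 300 mg Q4W".

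**Week 52 analysis.** IGA 0 or 1 at Week 52 is a secondary endpoint in both documents, and Protocol 10.2.3.2 assigns it to the logistic model. SAP Table FCAB.5.2 has a secondary Week 52 row comparing 600, 300, 150 and 50 mg with placebo in the maintenance population. In the copy used here that row is labelled IGA 0 and its method cell is blank, apparently merged with the row above; the issue is the same for either endpoint. Protocol 10.2.1.2 instead calls maintenance analyses exploratory and descriptive: "The proportion and 95% CI will be reported by treatment for categorical variables". SAP 5.2.1 analyzes efficacy as randomized.

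**The concern.** Rescue and loss of response rest on the same criterion, failure to reach EASI-25. A subject who fails it and is given a topical steroid is a nonresponder from then on. A subject who fails it and has the study regimen replaced stays eligible to count as a responder at Week 52, with nothing in either document to say for which group.

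What is at stake is the reading of Week 52 IGA and of the maintenance proportions by treatment. Protocol 5.4 gives durability of response and dose selection for later studies as purposes of this period. If response regained on active or higher-dose drug counts for placebo or a lower dose, those groups look better than they are, and the difference from continued or higher dosing shrinks.

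**Working it through.** **1. The plan's own figure.** The only stated operating figure is for Week 16: 36% versus 8%, 50 per arm, two-sided Fisher's exact test at 0.05, power at least 90%. Exact enumeration of the two binomials gives 91.4%, so the figure is reproduced. The switches start only after induction, so it is not affected. The documents give no figure for Week 52.

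**2. Where post-switch response lands under each possible grouping.**

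| Grouping at Week 52 | Consequence |
|---|---|
| As randomized at Week 0 (SAP 5.2.1 default) | Response on 300 mg counts for placebo; response on 600 mg counts for placebo, 50 mg or 150 mg. A withdrawn and restarted responder counts for the original dose, not for placebo. No 300 mg group can exist. |
| Regimen at the start of maintenance | Response after relapse and restart counts for placebo; response after reassignment to 600 mg counts for the lower regimen. End-of-induction reassignments count in their new group. |
| Regimen at Week 52 | Response counts for the new regimen, but groups are selected by outcome: 600 mg takes in subjects who failed another regimen, and placebo keeps those who never relapsed. |

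The 300 mg group in SAP Table FCAB.5.2 can be formed only by reassignment, so the table cannot follow Week 0 randomization throughout. Neither document says which of the other groupings is meant, or who makes up the placebo group.

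**3. Illustration for withdrawal placebo, grouped by regimen at the start of maintenance.** Both rates are assumptions.

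Overstatement = P(relapse before Week 52) × P(IGA 0/1 at Week 52 after restart)

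- Low: 0.30 × 0.20 = 0.06
- Middle: 0.50 × 0.36 = 0.18
- High: 0.70 × 0.50 = 0.35

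Reassignment to 600 mg, if 40% of a lower regimen moves and 20% of those respond: 0.40 × 0.20 = 0.08.

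These products have no term for rescue. A switched subject who is also rescued is already a nonresponder. If half were rescued (an assumption), 6 to 35 points becomes 3 to 17.5, and 8 becomes 4.

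**4. Illustration for the placebo arm, grouped as randomized.** Let s be the share of the placebo arm moved to active drug and q the response rate after the move, both assumed. The Week 16 planning rates are carried to Week 52, the active arm is held at 36%, and 50 per arm is kept; all three are simplifications.

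Apparent placebo rate = 0.08 + s × q

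| s | q | Apparent placebo rate | Difference from 36% (points) | Fisher power |
|---|---|---|---|---|
| switch counted as nonresponse | – | 8% | 28 | 91.4% |
| 0.5 | 0.10 | 13% | 23 | 71% |
| 0.7 | 0.20 | 22% | 14 | 27% |
| 0.7 | 0.36 | 33.2% | 2.8 | 4% |
| 0.9 | 0.36 | 40.4% | −4.4 | 5% |

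The table shows how sensitive the comparison is to the missing rule. It does not forecast the result.

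**The case against.** The strongest case on the other side has five parts.

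- **Grouping.** A reader might infer that post-switch response is, as a fact of the plan, credited to the regimen that failed. The documents do not support that. Grouping is undefined, the as-randomized default sends a withdrawn and restarted subject to the original dose, and the 300 mg group shows that at least some switched subjects leave their earlier group. This stands.
- **Overlap with rescue.** Relapsers and subjects with persistent activity meet the rescue criterion, and those rescued are already nonresponders. This stands and lowers any estimate. It does not close the gap, because rescue is at the investigator's discretion.
- **Treatment policy.** Restart on relapse is part of the assigned strategy, and comparing continued dosing with withdrawal and retreatment on observed outcomes is a legitimate question. Topical rescue is also non-study therapy, so treating it differently is not an error in itself. This stands in part: the observed-outcome result deserves reporting. But the planned table is labelled as dose versus placebo, not as a comparison of strategies.
- **Stakes.** Protocol 10.2.1.2 calls maintenance analyses descriptive, and Protocol 10.2.3.3 plans Kaplan–Meier curves for loss of response, which a later switch cannot turn into success. Both limit the harm. However, the SAP does not carry those curves over, they do not cover Week 52 IGA, and a descriptive proportion has the same ambiguity as a modelled one.
- **Missing values as a remedy.** Setting post-switch continuous values to missing would take relapsers out of the descriptive summaries and flatter the failing regimen. This stands, and the fix below avoids it.

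**Conclusion.** The concern holds in a limited form. Both nonresponder rules omit the plan's failure-triggered switches, and the Week 52 groups are not defined. Followed as written, the Week 52 comparison with placebo can count post-switch response as success for a regimen that failed (as-randomized grouping or grouping by regimen at the start of maintenance), or it compares groups selected by outcome (grouping by current regimen).

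The size cannot be derived from the documents. The 6 to 35 points for the withdrawal group and the apparent placebo rates of 13% to 40% rest on assumed relapse, switch and retreatment response rates, and neither range allows for rescue. Reading them as estimates of bias would go too far. So would extending the concern to Week 16: the primary endpoint and the Week 16 secondary endpoints are unaffected. The correction is worth making before unblinding because Week 52 IGA is a named secondary endpoint and the change is cheap.

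**What to change.** 1. Define the maintenance analysis groups by the regimen assigned at the start of maintenance. Keep responders re-randomized to placebo apart from placebo responders continuing placebo, and name the Week 52 placebo comparator. Only the 2:1 re-randomization within responders gives a randomized contrast; say so beside the other comparisons.
2. Add to SAP 5.4.1 and Protocol 10.2.1.1: for categorical maintenance endpoints, a failure-triggered switch of study drug is nonresponse for the assigned maintenance regimen from the switch onward.
3. Report observed response regardless of switch as supportive, and post-switch response separately by regimen received and time since the switch.
4. For continuous measures, do not simply set post-switch values to missing. Show values up to the switch with the number switched, or carry the last pre-switch value forward, and show post-switch values separately.
5. Carry the Kaplan–Meier loss-of-response analysis of Protocol 10.2.3.3 into the SAP.
6. Reconcile the conflicting passages: the destination of 150 mg nonresponders (300 mg in Protocol 5.1, 600 mg in SAP 4.1); the start of maintenance (Week 16 in Protocol 5.1 and SAP 5.2.1, Week 20 in SAP 4.1); the definition of persistent disease activity (SAP 4.1 adds an 8-week condition); and whether Week 52 is descriptive (Protocol 10.2.1.2) or modelled (Protocol 10.2.3.2, SAP Table FCAB.5.2).

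Cost: short additions to the SAP and protocol text and one extra set of tables, with no new data. Week 52 proportions will be less favourable for groups with many switches.
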